8.2 Study Drug Exposure

The study will be packaged in a way that each dose will be 2 capsules/row, with the following blinded configuration for each treatment arm:

Due to the nature of this study and data collection, it will be assumed each capsule taken by the subjects will have equal treatment weight for study drug compliance and exposure. After database lock and when the study drug treatment is unblinded, each kit number assigned to a subject will be

verified that correct treatment arm was given based on the randomization schedule. Any incorrect treatment arm kit given where the estimated number of capsules taken defined in Section 8.1 is greater than zero, will be defined as a major protocol deviation. Study drug exposure will be listed and summarized based on the treatment arm subjects received. Any combinations of different treatment arms may be identified (i.e. receiving 50 mg of NYX-2925 dose for kit and receiving 200 mg of NYX-2925 dose for another kit).

The number of study days of study drug exposure will be summarized using descriptive statistics based on the date of the last dose of study drug collected in the subject disposition CRF page. If the last dose of study drug was not collected in the subject disposition CRF page, the last date of study drug returned will be used as the estimated date. If a subject does not return study drug after being dispensed study drug and the date of the last dose of study drug was not collected, then the number of study days will be set to missing.

8.3 Rescue Medication

Subjects will also be dispensed 1 bottle of acetaminophen to be used as rescue medication at visits Screening, Week 0 (Baseline), and Week 2. Each bottle will contain either 100 or 175 caplets and this amount will be collected on the CRF. Rescue medication will consist of 500 mg caplets of acetaminophen. Subjects will be instructed that up to 2 g/day of rescue medication are allowed and should be reported daily via their study issued handheld device.

The following data will be collected and derived at each start and end to the rescue medication accountability visit intervals:

Parameter	Origin/Derivation
Caplets Dispensed Amount	CRF
Caplets Returned Amount	CRF
Estimated Number of Days Taken	Derived: Date Returned – Date Dispensed + 1 (where the maximum would be the number of caplets issued at each dispensing visit)
Estimated Number of Caplets Taken	Derived: Number of Caplets Dispensed Amount – Number of Caplets Returned Amount
Average Rescue Medication Taken (g/day)	Derived: 0.5 x Estimated Number of Caplets Taken / Estimated Number of Days Taken (rounded off by two numbers after the decimal point)

The Overall Post-Baseline Average Rescue Medication Taken (g/day) will be calculated as:

 $0.5 \times \Sigma$ (Estimated Number of Caplets Taken After Dispensed at the Baseline Visit) / Number of Study Days at the Week 4/Early Termination Visit (rounded off by two numbers after the decimal point)

Descriptive statistics will be summarized for average rescue medication taken (g/day) by returning analysis visits Baseline, Week 2, Week 4, and Overall Post-Baseline.

Any rescue medication not returned during a subject's visit where rescue medication accountability is assessed will be set to missing for analysis purposes. If the caplets returned amount was collected as

zero on the CRF and the CRF collected a comment that the rescue medication bottle was not returned, then the caplets returned amount will be set to missing for analysis purposes.

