5.3.3 Exploratory Efficacy Endpoints

Exploratory efficacy endpoints include:

- Use of rescue medication
- Percent of subjects achieving ≥30% and ≥50% pain reduction on the NRS average pain intensity from baseline (average of Days -7 to -1) to Week 4 (average of Days 22 through 28)
- Number of days to the first ≥30% reduction and first ≥50% reduction in the NRS average pain intensity
- Number of days to sustained pain reduction

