9.3 Exploratory Efficacy Endpoints

9.3.1 Use of Rescue Medication Subgroup Analyses

Boxplots will be produced for each treatment arm side-by-side for the mean change from baseline NRS scores assessing average pain intensity in the past 24 hours versus the average rescue medication taken (g/day) at the following analysis visits:

- Baseline (average of Study Days -7 to -1)
 - o Versus Rescue Medication from Screening to Baseline
- Week 1 (average of Study Days 1 to 7)
 - o Versus Rescue Medication from Baseline to Week 2
- Week 2 (average of Study Days 8 to 14)
 - o Versus Rescue Medication from Baseline to Week 2
- Week 3 (average of Study Days 15 to 21)
 - Versus Rescue Medication from Week 2 to Week 4
- Week 4 (average of Study Days 22 to 28)
 - Versus Rescue Medication from Week 2 to Week 4

Scatter plots will also be produced for each analysis listed above for the mean change from baseline NRS scores assessing average pain intensity in the past 24 hours versus the average rescue medication taken (g/day).

Daily rescue medication taken will be collected in the daily diary data for each subject. If a subject recorded the use of rescue medication, then the NRS score for that specific day will be set to the mean baseline value calculated for the NRS scores assessing average pain intensity in the past 24 hours. Otherwise, the individual NRS scores assessing average pain intensity in the past 24 hours will remain the same value as collected. As an additional exploratory analysis, mean NRS score assessing average pain intensity in the past 24 hours will be recalculated for the post-baseline analysis visits described in Section 5.4.2:

- Week 1 (average of Study Days 1 to 7)
- Week 2 (average of Study Days 8 to 14)
- Week 3 (average of Study Days 15 to 21)
- Week 4 (average of Study Days 22 to 28)

ANCOVA analyses using the mean change from baseline will be provided for Weeks 1, 2, 3, and 4 as described in Section 5.3.5.2. These results compared to the analyses stated in Sections 9.1.2 and 9.2.2 will assist in determining the impact use of rescue medication.

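### Rescue use is quantified only in roughly two-week bottle counts, so no planned output shows how often each randomized arm used it in the primary-endpoint week, and the overall g/day formula has no rule for an unreturned bottle

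*SAP*

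**What the plan says.** Protocol 5.3.3 lists "Use of rescue medication" among the exploratory efficacy endpoints, and protocol 12.5.2 plans a descriptive summary of it.

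SAP 8.3 obtains the amount used from bottles given out at Screening, Baseline and Week 2. On strength and bottle size it says "Rescue medication will consist of 500 mg caplets of acetaminophen" and "Each bottle will contain either 100 or 175 caplets and this amount will be collected on the CRF". The interval count is defined as "Derived: Number of Caplets Dispensed Amount – Number of Caplets Returned Amount". It is multiplied by 0.5 and divided by the return date minus the dispensing date plus 1. The overall post-baseline value is 0.5 times the sum in this expression: "Estimated Number of Caplets Taken After Dispensed at the Baseline Visit) / Number of Study Days at the Week 4/Early Termination Visit". For bottles that do not come back, the rule is "Any rescue medication not returned during a subject's visit where rescue medication accountability is assessed will be set to missing for analysis purposes".

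SAP 9.3.1 plots weekly change in pain against these g/day values. The entry for Week 3 and the entry for Week 4 are the same: "Versus Rescue Medication from Week 2 to Week 4". The Baseline panel sets Days -7 to -1 against the whole Screening-to-Baseline bottle.

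The same section notes that "Daily rescue medication taken will be collected in the daily diary data for each subject". Pain on a diary rescue day is replaced by the subject's baseline mean, and the ANCOVA is rerun at Weeks 1 to 4 (Table 14.2.1.2.5, Efficacy population).

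SAP 13 lists one table of rescue use, 14.3.5.5, in the Safety population. SAP 6.1 names rescue medication among the data assigned to the treatment actually received.

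**The concern.** Acetaminophen is open to every arm throughout Days 22-28, the week that defines the primary endpoint. If one arm takes more of it that week, its pain scores may fall for a reason other than study drug. A reader of the primary result therefore wants to know how often each randomized arm used rescue in those seven days. A bottle count spanning Week 2 to Week 4 cannot say.

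The overall g/day value raises a separate problem. Its denominator is fixed at all study days, while a lost bottle removes part of its numerator. The text does not say whether the remainder is still summed, so two programmers could follow it and produce different tables.

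**Working it through.** **Inputs.** Caplet strength 0.5 g, bottles of at least 100 caplets, the interval and overall formulas and the missing rule are from SAP 8.3. The limit of 2 g/day (4 caplets) is in both documents. Nominal visits are Days 1, 14 and 28 (protocol Table 3). Neither document gives a rescue-use rate or a bottle-return rate, so there is no rescue figure to reproduce. The use patterns and loss rates below are assumptions.

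**1. Can the Week 2-to-4 value describe Days 22-28?** Interval days = 28 - 14 + 1 = 15.
- Subject A takes 2 g/day on Days 22-28 only: 7 x 4 = 28 caplets, and 0.5 x 28 / 15 = 0.93 g/day.
- Subject B takes 2 g/day on Days 15-21 only: again 28 caplets and 0.93 g/day.

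One used rescue on every day of the endpoint week and the other on none, yet both have the same value. In the Week 4 plot they are indistinguishable on the rescue axis.

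**2. Overall value with one of two post-baseline bottles unreturned.** Take 2 g/day on all 28 days, 56 caplets from each bottle.
- Both returned: 0.5 x 112 / 28 = 2.0 g/day.
- One missing, term skipped: 0.5 x 56 / 28 = 1.0 g/day, half the true value.
- One missing, missingness propagates: no overall value.
- Caplets matched to the 14 days of the first bottle: 0.5 x 56 / 14 = 2.0 g/day.

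The Week 2 and Week 4 interval averages are not distorted on either reading. The affected one is simply missing.

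**3. Effect on an arm mean if the term is skipped.** Assume true use of 1 g/day for everyone and a share m of the arm missing one bottle. The mean is 1 - m/2.

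| m (assumed) | Reported mean, g/day |
|---|---|
| 5% | 0.975 |
| 10% | 0.95 |
| 20% | 0.90 |
| 30% | 0.85 |

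With 10% in one arm and 30% in another, a false difference of 0.95 - 0.85 = 0.10 g/day appears with equal true use.

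**4. Day counting.** The interval days add to 14 + 15 = 29, because Day 14 falls in both intervals. The overall formula uses 28.

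**5. Baseline panel.** The plotted quantity is change from baseline in the mean pain score. At Baseline this is the baseline mean minus itself, zero for every subject. The rescue value beside it can cover up to 4 weeks of screening, against 7 days of pain scores.

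**The case against.** The strongest reply is that rescue use is exploratory, the protocol promised only a descriptive summary, and SAP 8.3 provides one. Three parts of the case against the point stand.

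First, a reader might infer that the SAP understates rescue use. The text does not establish this. Skipping a missing bottle amounts to counting it as zero caplets, which is an imputation. SAP 5.5.2 imputes no safety values, and no efficacy values beyond those specified. SAP 5.1.3 provides a not-reported category for values that cannot be calculated. Those sections lean towards a missing overall value, so halving is possible but not certain.

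Second, a reader might suppose that heavy users empty and discard their bottles, making losses informative. At the 2 g/day limit, 14 days uses 56 caplets from a post-baseline bottle of at least 100, leaving 44 or more. The documents give no support for that mechanism.

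Third, a reader might conclude that rescue is handled from bottle returns alone and cannot be examined by arm at Week 4. SAP 9.3.1 does use the diary, in a between-arm ANCOVA that includes Days 22-28, and its g/day plots are side by side by arm in the Efficacy population. The ANCOVA bears directly on whether rescue alters the pain comparison. However, it returns adjusted pain differences and does not report how often rescue was taken, so the descriptive gap remains.

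The contrast with SAP 8.1 also needs care. That section sets overall study-drug compliance to missing when drug is not returned, and it matches summed intervals in numerator and denominator. It also treats unreturned drug as taken, so it is a partial model only.

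**Conclusion.** The point holds as a gap in describing an exploratory endpoint and as an unspecified derivation rule. No planned output gives the frequency of rescue use by randomized arm in Days 22-28. The two-week g/day value cannot supply it: opposite patterns across Weeks 3 and 4 both give 0.93 g/day. The single rescue table is by treatment received. That differs from the randomized Efficacy population only for subjects given a wrong kit or falling outside that population, and the documents do not say how many there are.

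The overall g/day value for a subject with even use and one of two bottles missing is either half the truth or absent, depending on a choice that the SAP leaves open. On the skipping reading, and assuming equal use and 5% to 30% of an arm affected, the arm mean is low by 2.5% to 15%. On the other reading these subjects leave the overall summary and the remaining values are not understated. The Baseline panel carries no information on pain as specified.

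None of this touches the primary model, the sample size or the power.

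**What to change.** 1. In SAP 9.3.1, add an exploratory table by randomized arm in the Efficacy population. It should give the percentage of diary days with rescue use at Baseline (Days -7 to -1) and in each of Weeks 1 to 4, with the Week 4 active-minus-placebo difference and 95% CI. State that the denominator is completed diary days.
2. In SAP 8.3, say how an unreturned bottle enters the overall value. Either divide by the days of the intervals with a returned bottle, counting each visit day once so that complete returns still give 28 days, or set the overall value to missing when any post-baseline bottle is not returned.
3. In the Baseline panel of SAP 9.3.1, plot the baseline mean pain score, not its change.

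The cost is one table from diary data already collected and a few sentences of SAP wording before database lock. The drawback is that the diary item is yes/no and carries no amount. Keep the bottle-based g/day in the tables and plots, and place the diary percentages beside it.

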8.4 Prior and Concomitant Medications

Prior and concomitant medications will be coded using the World Health Organization Drug Dictionary (WHO-DD), version 03-2016 and will be classified according to the default Anatomical Therapeutic Chemical (ATC) classification system code (up to 4 levels), WHO-DD Drug Name, and Preferred Term (PT).

Due to the nature of this study, the date and time of first dose of study drug was not collected on the CRF. Therefore, the following algorithm will be used to determine prior medications:

• Earliest Possible Medication Start Date ≤ Baseline Visit Date

The following algorithm will be used to determine concomitant medications:

• Latest Possible Medication Stop Date ≥ Baseline Visit Date

Depending on the start and stop dates of the medication, it is possible for a medication to be classified as both prior and concomitant.

Prior and concomitant medications will be summarized by the ATC Class Level 3 category (or Level 2 if there is not an applicable Level 3 category) and PT. Subjects may have more than one medication per ATC category and PT. At each level of subject summarization, a subject will be counted once if he/she reports one or more medications at that specific level. The prior medication frequency distribution table will be displayed by the safety treatment arms and all subjects even though the prior medication information was collected prior to dispensing study drug.

Concomitant medications identified on the CRF as the 1 protocol allowed analgesic medication will be repeated in an additional subject listing and summary table.

9. Efficacy Analyses

In the event efficacy data was collected more than once within the same day, the latest complete set of assessment data will be used for the analyses. All unused multiple assessments for efficacy collected within the same date will be presented in the subject listings. Any efficacy assessments that were collected more than once within the same day will be documented in the SDTM Study Data Reviewer's Guide.

9.1 Primary Efficacy Data

The primary efficacy data for this study is the NRS score assessing average pain intensity in the past 24 hours. Daily collected pain scores are based on an 11-point numerical rating scale/Likert scale ranging from 0 to 10. Where 0 represents no pain and 10 is the worst pain imaginable^[2].

The mean NRS score assessing average pain intensity in the past 24 hours will be calculated for the analysis visits described in Section 5.4.2^[4]:

- Baseline (average of Study Days -7 to -1)
- Week 1 (average of Study Days 1 to 7)
- Week 2 (average of Study Days 8 to 14)
- Week 3 (average of Study Days 15 to 21)
- Week 4 (average of Study Days 22 to 28)

The mean baseline visit will be calculated if at least 6 of the study days have a reported pain score. This is a requirement in order to be eligible for being randomized to a study drug treatment arm. There will need to at least 4 daily pain scores collected within a post-baseline analysis visit in order to calculate the mean pain score for that visit.

Each mean analysis visit score will take on values ranging from 0 to 10 and will be rounded off by one number after the decimal point. Data prior to Study Day -7 or after Study Day 28 will not be used in the mean calculated scores. No missing data imputations will be used for these observed means, but Section 9.1.3 will explain imputation methods used for sensitivity analyses.

The actual means, change from baseline, and percent change from baseline at each analysis visit will be summarized using descriptive statistics. The same descriptive statistics table will be additionally provided by each study site, age groups, gender, race, ethnicity, and subjects using or not using at least 1 concomitant analgesic medication at Baseline. All data collected and derived will be presented in subject listings.

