5.3 Study Endpoints

5.3.1 Efficacy Endpoints

The primary endpoint is the change in the numerical rating scale (NRS) score assessing average pain intensity in the past 24 hours from baseline (average of Days -7 to -1) to Week 4 (average of Days 22 through 28).

Secondary efficacy endpoints include:

- Change in the mean NRS score for daily worst pain intensity from baseline (average of Days -7 to -1) to Week 4 (average of Days 22 through 28)
- Change in the mean NRS score assessing average pain intensity in the past 24 hours from baseline (average of Days -7 to -1) to each week of treatment (average of Days 1 through 7, Days 8 through 14, and Days 15 through 21)
- Change in the mean NRS score assessing average pain upon walking intensity in the past 24 hours from baseline (average of Days -7 to -1) to each week of treatment (average of Days 1 through 7, Days 8 through 14, Days 15 through 21, and Days 22 through 28)
- Patient Global Impression of Change (PGI-C) at Weeks 2 and 4
- Change in published subscale scores of the Short-Form McGill Pain Questionnaire version 2 (SF-MPQ-2) from baseline (Visit 2) to Week 4
- Change in published subscale scores of the Norfolk Quality of Life Questionnaire Diabetic Neuropathy (QOL-DN) from baseline (Visit 2) to Week 4
- Change in the Insomnia Severity Index from baseline (Visit 2) to Week 2 and Week 4
- Change in published subscale scores of the Hospital Anxiety and Depression Scale (HADS) from baseline (Visit 2) to Week 4

- Change in the mean Daily Sleep Interference Scale (DSIS) score from baseline (average of Days -7 to -1) to each week of treatment (average of Days 1 through 7, Days 8 through 14, Days 15 through 21, and Days 22 through 28)
- Change in the Brief Pain Inventory for Diabetic Peripheral Neuropathy (BPI-DPN) from baseline (Visit 2) to Week 4

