One week following the Week 2 visit, subjects will be contacted by telephone for an assessment of adverse events and to reinforce diary completion.

Treatment Period (Week 4/Early Termination, Visit 4)

During the Week 4 or Early Termination Visit, subjects will be evaluated for compliance with study medication, and return all materials and unused study medication/rescue medication to the study site. The study-issued handheld device will be returned. Pain diary compliance will be reviewed by the study staff. Adverse events will be assessed by asking the subject a non-leading question; for example, "Have you experienced any new or changed symptoms since we last asked/since your last visit?" Use of concomitant medications will be documented. Vital signs (sitting blood pressure and pulse after 5 minutes) and body weight will be measured, brief physical examination performed, and subjects will undergo a 5-minute electrocardiogram. Blood and urine samples will be collected for chemistry, hematology, and urinalysis testing. Female subjects of childbearing potential will be tested for pregnancy using a local urine testing kit. Subjects will undergo drug and alcohol screen using a local urine testing kit and breathalyzer, respectively.

[figure not shown]
Scales to be completed at the Week 4/Early Termination Visit include BPI-DPN, PGI-C, SF-MPQ-2, HADS, QOL-DN, Insomnia Severity Index, and S-STS.

Follow-Up Visit (Week 5/7 days Post-Treatment, Visit 5)

Subjects will return to the study site 7 days following the Week 4/Early Termination visit to assess adverse events and concomitant medication use. The adverse event assessment will include any serious adverse events that were ongoing at the time of study completion, and

whether any ongoing adverse events had progressed to becoming serious. Blood samples will be collected for liver function testing.

Figure 1: Study Design

pDPN = painful diabetic peripheral neuropathy; Wk = week

Table 3: Schedule of Procedures

| Study Period | Screening | Baseline | Treatment | | Follow-Up |
|---|---------------------------|-------------------------|-----------------|------------------------------|-----------------|
| Study Week (Day) | (-28 to -1) | Week 0 (1) ^b | Week 2 (14 ± 2) | Week 4 ^c (28 ± 2) | Week 5 (35 ± 2) |
| Study Visit | Visit 1 | Visit 2 | Visit 3 | Visit 4 | Visit 5 |
| Assessment | | | | | |
| Informed consent prior to any study procedure | X | | | | |
| Assess inclusion/exclusion criteria | X | X | | | |

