| Insomnia Severity Index | | X | X | X | |
| Hospital Anxiety and Depression Scale (HADS) | X | X | | X | |
| Patient Global Impression of Change (PGI-C) scale | | | X | X | |
| Sheehan Suicidality Tracking Scale (S-STS) | X | X | X | X | |
| Concomitant medications | X | X | X | X | X |
| Adverse events ^o | X | X | X | X | X |

- a) Subjects will discontinue all but 1 allowed concomitant pharmacologic analgesic medication. Duration of the period will depend upon the analgesic treatment(s) being discontinued (not to exceed 4 weeks). Subjects taking no more than 1 allowed concomitant analgesic medication at Visit 1 may directly begin Week -1 of the Screening Period.
- b) Visit window for Baseline Visit is 6 to 10 days after start of Week -1
- c) Subjects who prematurely discontinue randomized treatment will have Week 4 procedures performed.
- d) Review of these educational materials may be repeated for some or all subjects or depending on findings of an ongoing blinded data review (e.g., if pain score variability is increased on a subject or site level).
- e) Vital signs will include blood pressure and pulse after at least 5 minutes of being seated, and prior to blood sample collection.
- f) A complete physical examination will be performed at Visit 1 and a brief physical examination will be performed at Visits 2 and 4. The physical examination at Visit 1 will include a comprehensive neurological examination.
- g) If the screening hepatitis C antibody test result is reactive, a nucleic acid test for hepatitis C virus-ribonucleic acid (HCV RNA) should be performed for confirmation of chronic infection. If the screening HIV test is positive, a confirmatory Western Blot test should be performed to confirm HIV status.
- h) Urine drug screen and alcohol breathalyzer.

- i) Samples will be obtained following an 8-hour fast. The Week 2 and Week 5 samples will only be analyzed for liver function tests and no fasting will be required. HbA1c will be collected at Screening (Visit 1) only.
- i) Analgesic medications discontinued during the Screening Period cannot be restarted until after the Week 4 visit.
- k) Numerical Rating Scale of pain intensity (0 = no pain to 10 = worst pain imaginable) will be completed once daily at bedtime. At Visit 1, average pain intensity over the past 24 hours will be recorded onto device by site personnel.
- 1) Subjects will be instructed to take no more than 2 g/daily (one to two 500-mg caplets every 4 to 6 hours as needed) for pain.

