10.3 Treatment Period (Week 2 and Week 4)

10.3.1 Week 2 (Visit 3)

At Visit 3, the following procedures and assessments will be performed:

- Concomitant medication use assessed
- Adverse events assessed
- Sitting vital signs (blood pressure and pulse after 5 minutes)
- Serum chemistry for liver function testing (only)
- PGI-C
- Insomnia Severity Index
- Rescue medication supplies returned, appropriate use assessed, and compliance/accountability performed
- Investigational product and supplies returned and compliance/accountability performed
- Compliance with entry of pain intensity and rescue medication into daily diary
- Investigational product dispensed
- Rescue medication dispensed

Subjects will be reminded on how to record their pain on the device

Subjects will also be reminded about appropriate expectations around their participation in a clinical study

Review of these educational materials may be repeated for some or all subjects depending on findings of an ongoing blinded data review (e.g., if pain score variability is increased on a subject or site level. On each of day until returning to the study site at Week 4, subjects will record the following on the handheld device:

- At bedtime: average pain intensity, worst pain intensity, pain on walking, and use of rescue medication during the past 24 hours.
- Upon waking: DSIS

The investigative site staff will contact study subjects by telephone one week following Week 0 to reinforce the diary completion and assess adverse events.

Subjects will be instructed to return to the study site at Week 4.

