5.1.2 Study Day

Study day will be calculated in reference to Day 1 stated above in Section 5.1.1. For assessments conducted on or after the Day 1 date, study day is calculated as the assessment date – Day 1 date + 1. For assessments conducted before the Day 1 date, study day is calculated as the assessment date – Day 1 date. There is no Study Day 0 in this study.

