5.4.2 Efficacy NRS Pain Intensity Scores Analysis Visits

These analysis visits are for the daily diary data when the study-issued handheld devices where provided on Visit 1 (screening) until the devices are returned on the Week 4 or Early Termination visit.

Protocol and/or CRF Term	Analysis Visit	Study Day Window
Visit 1/Screening/Weeks -4 to -1	Screening ^(a)	≤ Day -8
Visit 1/Screening/Weeks -4 to -1	Baseline	Day -7 to Day -1
Visit 2/Baseline/Week 0	Week 1	Day 1 to Day 7
Visit 3/Week 2	Week 2	Day 8 to Day 14
N/A	Week 3	Day 15 to Day 21
Visit 4/Week 4	Week 4	Day 22 to Day 28
N/A	After Day 28 ^(b)	Day 29 or Later

⁽a) Screening values will be displayed in listings, but not included summary tables.

⁽b) Data collected after Day 28 will be displayed in listings, but not included summary tables with an analysis visit.

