9.3.4 Number of Days to Sustained Pain Reduction

If a subject reaches a responder status at any point of the study as defined in Section 9.3.3, the following additional conditions will also need to be met in order for the subject to be considered as sustaining pain reduction:

Protocol No.: NYX-2925-2001

- At least 8 days from the onset of the response to the last collected pain score that is \leq Study Day 28.
 - o Study Day 21 is the latest possible day for sustained pain reduction if the study day NRS score assessing average pain intensity in the past 24 hours was collected.
- The responder status endpoint of interest stated in Section 9.3.2 must by met at the Week 4 analysis visit.
 - Responder at ≥30% Pain Reduction
 - o Responder at ≥50% Pain Reduction
- Once the responder status has been met, the remainder of the study days after the last day in the 4-day interval until Study Day 28 will calculate the overall remaining mean for NRS score assessing average pain intensity in the past 24 hours. If the overall remaining mean score shows a pain reduction \geq to the responder status (i.e. \geq 30% or \geq 50%), then this criteria of the sustained pain reduction will be met.

A frequency distribution of these categories will be summarized:

- >30% Pain Reduction Status
 - Never Reached
 - o Reached, but did not Sustain
 - Reached and Sustained at Mean Analysis Visit Week 4 (Responder Endpoint)
- >50% Pain Reduction Status
 - Never Reached
 - o Reached, but did not Sustain
 - Reached and Sustained at Mean Analysis Visit Week 4 (Responder Endpoint)

The number of days of onset to sustained pain reduction will be summarized using descriptive statistics. The same Cox proportional hazards modeling analyses and Kaplan-Meier probability plot described in Section 9.3.3 will be applied to sustained pain reduction data. The number of days to sustained pain reduction will be based on the observed daily pain scores and will not use any imputation methods for missing data described in Section 9.1.3.

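### The diary is handed back at Visit 4, which may fall on Days 26–28, so only 4 to 6 of the seven Day 22–28 scores can exist and the tolerance for missed entries depends on the appointment date

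*SAP*

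**What the plan says.** **Endpoint.** Protocol 5.3.1 defines the primary endpoint as the change in average pain from baseline "to Week 4 (average of Days 22 through 28"). SAP 5.4.2 and 9.1 use the same fixed calendar window. From the baseline visit onward, "study day is calculated as the assessment date – Day 1 date + 1" (SAP 5.1.2), so the baseline visit is Day 1.

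**Diary.** The pain scale "will be completed once daily at bedtime" (Protocol Table 3, footnote k). A score entered by site staff is described for Visit 1 only. After Visit 3, Protocol 10.3.1 says: "On each of day until returning to the study site at Week 4, subjects will record the following on the handheld device". At the Week 4 visit, "The study-issued handheld device will be returned" (Protocol 6.1; also listed in 10.3.2). SAP 5.4.2 likewise describes diary data as running "until the devices are returned on the Week 4 or Early Termination visit". The schedule table marks bedtime recording under Visits 1 to 3 and not under Visit 4.

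**Visit window.** Protocol Table 3 and SAP Appendix I place Visit 4 at Day 28 ± 2, that is, Days 26 to 30.

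**Minimum data.** SAP 9.1: "There will need to at least 4 daily pain scores collected within a post-baseline analysis visit" for the mean of that visit to be calculated. The observed means are not imputed. A subject without a Week 4 mean is set to non-responder (SAP 9.3.2) and cannot be in the Per Protocol population (SAP 6.3).

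**The concern.** The endpoint window closes on the evening of Day 28, but the device is handed back at a visit that may take place on Day 26, 27 or 28. Even a visit on the nominal Day 28 comes before that evening's entry. The seven-day mean that the protocol defines can be fully observed only when the visit falls in the late part of its window.

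Missing primary data are at stake. A subject seen early in the window has little or no margin for a missed entry, while one seen on Day 29 or 30 can miss three evenings and keep the Week 4 mean. A subject without that mean contributes nothing to the primary ANCOVA, leaves the Per Protocol population and counts as a non-responder, even if treatment and Visit 4 were completed on time. Worst pain and pain on walking follow the same averaging rule (SAP 9.2.1, 9.2.3) and share the problem.

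**Working it through.** **Step 1: the plan's own figure.** SAP 4.4 gives 75 subjects per group, a difference of 1.05, an SD of 2.25, two-sided alpha of 0.05 and power of about 80%. The noncentrality is 1.05 / (2.25 × √(2/75)) = 2.86. Power is 81.0% by the noncentral t and 81.5% by the normal approximation, so the stated figure reproduces. SAP 4.4 states no dropout allowance.

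**Step 2: scores that can exist.** With Visit 4 on Day v and the device returned then, the last bedtime entry is on Day v − 1. The most Week 4 scores possible is m = min(28, v − 1) − 21.

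**Step 3: tolerance.** The mean needs at least 4 scores, so it is lost once m − 3 entries are missed.

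**Step 4: chance of no Week 4 mean.** This is P(X ≤ 3) for X binomial(m, p), where p is daily completion and days are taken as independent. The documents give no post-baseline completion rate, so p is an assumption and is shown over a range. At p = 0.90:
- Day 26: 1 − 0.9⁴ = 1 − 0.6561 = 0.344.
- Day 27: 1 − (0.9⁵ + 5 × 0.9⁴ × 0.1) = 1 − (0.5905 + 0.3281) = 0.081.

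| Visit 4 | Most scores (m) | Missed entries that remove the mean | p = 0.95 | p = 0.90 | p = 0.80 |
|---|---|---|---|---|---|
| Day 26 | 4 | 1 | 18.6% | 34.4% | 59.0% |
| Day 27 | 5 | 2 | 2.3% | 8.1% | 26.3% |
| Day 28 | 6 | 3 | 0.2% | 1.6% | 9.9% |
| Day 29 or 30 | 7 | 4 | 0.02% | 0.3% | 3.3% |

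The counts assume that no pain score is taken at the clinic on the visit day, and neither document provides for one during treatment. If one were taken, Days 26, 27 and 28 would give 5, 6 and 7.

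**Step 5: effect on power, for scale only.** If 5%, 10% or 20% of each arm had no Week 4 mean, the analyzed number per arm would be 71.2, 67.5 or 60.0. Power by the noncentral t would be about 79%, 77% or 72%, with the difference and SD unchanged. These losses are illustrative. The share of visits on each day is not given, so the actual loss cannot be derived.

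**The case against.** **Short weeks are a stated choice.** The four-score rule tolerates three absent days. The worked example in SAP 9.1.3 treats scores on Days 22 to 25 as a valid Week 4 mean, which is exactly what a Day 26 visit yields with a complete diary. This stands: the plan does not contradict itself on whether a short week counts. The example does not address an in-window visit that leaves no margin.

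**The appointment alone removes nothing.** A reader might infer that fully adherent completers lose the endpoint because of their visit date. The documents do not support that. Every in-window visit leaves at least four possible scores, and loss needs one to three missed evenings as well when the visit is on Days 26 to 28. What the date changes is how many misses are forgiven.

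**Other analyses cover the gap.** Multiple imputation, LOCF and BOCF (SAP 9.1.3) fill a Week 4 mean that could not be calculated, and the MMRM (SAP 9.2.2) keeps these subjects through their earlier weeks. This stands in part. All four lie outside the primary analysis, and none restores responder status or Per Protocol membership.

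**Completion may be high.** A baseline mean needs 6 of 7 daily scores for randomization, and compliance is reviewed at visits and reinforced by phone. That favors the better columns of the table, but the Day 26 figure is 18.6% even at 95% completion.

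**Bias between arms.** A reader might infer a biased treatment comparison. Treatment is blinded, and nothing in the documents suggests that visit dates or missed entries differ by arm.

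**Sustained reduction.** SAP 9.3.4 says "Study Day 21 is the latest possible day for sustained pain reduction", and a reader might see a contradiction, since a Day 28 score often cannot exist. The SAP makes that statement conditional on the score having been collected, and the endpoint is exploratory. It is not a separate error.

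**Conclusion.** The mismatch is real and follows from the documents without any assumption about behavior: visits on Days 26, 27 and 28 allow at most 4, 5 and 6 of the seven endpoint scores. The consequence is conditional. A Week 4 mean is lost only when entries are also missed, and the number needed falls from four to one as the visit moves from Days 29–30 to Day 26.

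Per subject, the chance of loss runs from 0.3% to 34% across the window at 90% completion. Those figures rest on an assumed completion rate and on independence between days. No overall percentage is defensible, because the documents give neither the completion rate nor the distribution of visit dates. The likely harm is avoidable missing primary data and some completers classed as non-responders, with a modest cost in power. It is worth correcting because the correction is nearly free. The stated power is not itself in error.

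**What to change.** Reconcile the Visit 4 and device-return window with the endpoint window in Protocol Table 3, Protocol 10.3.2 and SAP Appendix I, so that the Day 28 bedtime entry is made before the device is returned. The cost is a small schedule edit and a slightly later or narrower visit window. The endpoint definition and the four-score rule can stay as they are.

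A tempting alternative is to leave the schedule alone and substitute the last seven diary days before Visit 4 when the fixed window holds fewer than four scores. I would not do this:
- It changes the protocol-defined window for subjects selected by missingness.
- For a Day 26 visit it uses Days 19 to 25, so Days 19 to 21 would count in both Week 3 and Week 4.
- For a Day 30 visit it would use Days 23 to 29, which conflicts with the bar in SAP 9.1 on data after Study Day 28.
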